4.5 Safety Variables

4.5.1 Adverse Events and Serious Adverse Events Variables

Adverse events and serious adverse events will be collected from the time of informed consent signature and then at each visit until the end of the study. All adverse events are to be coded to a “PT”, “High Level Term (HLT)”, “High-level Group Term (HLGT)” and the associated primary “SOC” using the version of MedDRA currently in effect at Sanofi at the time of database lock.

An adverse event (AE) is any untoward medical occurrence in a patient or clinical investigation patient administered a pharmaceutical product and which does not necessarily have to have a causal relationship with this treatment.

A serious adverse event (SAE) is any untoward medical occurrence that at any dose results in death; is life-threatening; requires inpatient hospitalization or prolongation of existing hospitalization; results in persistent or significant disability/ incapacity; is a congenital anomaly/ birth defect; or is a medically important event.

An adverse event of special interest (AESI) is an AE (serious or nonserious) of scientific and medical concern specific to the sponsor's product or program, for which ongoing monitoring and immediate notification by the Investigator to the sponsor is required. Such events may require further investigation in order to characterize and understand them. Adverse events of special interest may be added or removed during a study by protocol amendment.

Laboratory, vital signs or ECG abnormalities are to be recorded as AEs only if

- Symptomatic, and/or
- Requiring either corrective treatment or consultation, and/or
- Leading to IMP discontinuation or modification of dosing, and/or
- Fulfilling a seriousness criterion, and/or
- Defined as an AESI

Pretreatment AEs are defined as AEs that developed or worsened during the pre-treatment period. Treatment emergent adverse events (TEAEs) are defined as AEs that developed or worsened during the treatment-emergent period.

4.5.2 Laboratory Safety Variables

Hematology, chemistry, urinalysis, and serum pregnancy testing samples will be analyzed by a central laboratory. The urine pregnancy test kit will be provided to the site by the laboratory.

Blood samples for serum chemistry and hematology testing will be collected at screening (day -7 to day -35), baseline (Day 1), Week 8, Week 16 (EOT), Week 28 (EOS), ET and unscheduled visits. Total basophil and eosinophil counts are of particular interest in AD patients, due to the occurrence of basophil histamine release and eosinophilia in this population. Understanding the lymphocyte profiles of AD patients may help researchers understand disease heterogeneity. Blood samples should be collected after a 6 to 8 hour fast, if possible; fasting is not mandatory.

Blood Chemistry

Sodium	Total protein (serum)	Total bilirubin
Potassium	Creatinine	Total cholesterol
Chloride	Blood urea nitrogen	Low-density lipoprotein
Carbon dioxide	Aspartate aminotransferase (AST)	High-density lipoprotein
Calcium	alanine aminotransferase (ALT)	Triglycerides
Glucose	Alkaline phosphatase	Uric acid
Albumin	Lactate dehydrogenase	Creatine phosphokinase (CPK)

Note: Direct and indirect bilirubin will be measured when the total bilirubin is above the upper limit of normal (ULN); CPK isoenzymes will be reflexly measured when CPK >5 ULN

Hematology with Differential

Hemoglobin	WBCs differential:
Hematocrit	Neutrophils
Red blood cells (RBCs)	Lymphocytes
White blood cells (WBCs)	Monocytes
Red cell indices	Basophils
Platelet count	Eosinophils

Urinalysis

Urine samples for urinalysis will be collected to measure overall patient health at screening (day -7 to day -35), baseline (Day 1), Week 16, Week 28 (EOS), ET and unscheduled visits.

Color	Glucose	RBC
Clarity	Blood	Hyaline and other casts
pH	Bilirubin	Bacteria
Specific gravity	Leukocyte esterase	Epithelial cells
Ketones	Nitrite	Crystals
Protein	WBC	Yeast

Note: Microscopic analysis will only be done in the event of abnormal dipstick results

Pregnancy testing (serum or urine) will be performed for all women of childbearing potential at screening (day -7 to day -35), baseline (Day 1), Week 4, Week 8, Week 12, Week 16 (EOT), Week 28 (EOS), ET and unscheduled visits.

4.5.3 Vital Sign Variables

The following vital signs parameters will be collected:

- Weight (kg) and height (cm)
- Respiratory rate (breaths/min)
- Heart rate (beats/min)
- Systolic and diastolic blood pressures (mmHg)
- Body temperature (°C)

Weight is determined at screening and baseline (Day 1), and Week 16 (EOT), Week 28 (EOS), ET and unscheduled visits. Height is only measure at screening. Other vital signs are collected pre-dose at every scheduled and unscheduled clinic visit.

4.5.4 12-Lead Electrocardiography (ECG) Variable

The ECG interpretation variable are dichotomized to normal and abnormal. Electrocardiograms will be performed before blood is drawn during visits requiring blood draws. A standard 12-lead ECG will be performed at screening, Week 16 (EOT), and Week 28 (EOS) or ET visits.

4.5.5 Physical Examination Variable

The physical examination variable values are dichotomized to normal and abnormal.

A thorough and complete physical examination will be performed at screening, Week 16 (EOT), and Week 28 (EOS) or ET visits. If patients have any symptom or sign of ocular surface diseases, eg, conjunctivitis and blepharitis, at screening or during study period, ophthalmological examinations should be done.

4.5.6 Immunogenicity Variables

The immunogenicity variables are ADA status, ADA titer and anti-dupilumab neutralizing antibodies (NAb) status.

Immunogenicity will be characterized by ADA responses and titers observed in patients in the ADA population.

ADA response categories are defined as follows:

- Negative in ADA assay at all time points analyzed
- Preexisting immunoreactivity
Defined as either an ADA positive response in the ADA assay at baseline with all post first dose ADA results negative, OR a positive response at baseline in the ADA assay with all post first dose ADA results less than 4-fold baseline titer levels
- Treatment emergent response in the ADA assay
Defined as a positive response in the ADA assay post first dose when baseline results are negative or missing. The treatment emergent responses may be further characterized as Persistent, Indeterminate or Transient

- Persistent Response - treatment emergent ADA positive response with two or more consecutive ADA positive sampling time points separated by greater than 12-week period [greater than 85 days], with no ADA negative samples or any missing sample in between
- Indeterminate Response - treatment-emergent response with only the last collected sample positive in the ADA assay
- Transient Response - treatment emergent ADA positive response that is not considered persistent or indeterminate
- Treatment boosted response in the ADA assay
Defined as a positive response in the ADA assay post first dose that is greater than or equal to 4-fold over baseline titer levels, when baseline results are positive

ADA status are defined as follows:

- ADA positive patients, that is patients with treatment-emergent or treatment boosted response.
- ADA negative patients, that is patients with preexisting immunoreactivity or negative in the ADA assay at all time points.

Titer Category (Maximum titer values):

- Low (titer <1000)
- Moderate ($1000 \leq \text{titer} \leq 10\,000$)
- High (titer >10 000)

Serum samples for ADA will be collected at the clinic visits specified in [Appendix 10.2](#). ADA analysis will be conducted on sample collected at baseline, Week 16 (EOT), Week 28 (EOS), and ET. All samples that are positive in the ADA assay will be further characterized for ADA titers and for the presence of NAb. Samples that tested negative for ADA are considered to be NAb negative and are therefore not analyzed in the NAb assay. The NAb status is categorized as follows:

- Negative (samples negative in the ADA assay, and samples positive in ADA assay that are negative in the NAb assay)
- Positive (samples positive in both the ADA and NAb assays)

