10.1.5 Early Termination Visit

Patients who are withdrawn from the study before the primary endpoint visit (Week 16) will be asked to return to the clinic for 2 visits: once for early termination assessments, and again at Week 16 (primary endpoint visit), as described in [Section 10.1.2.6](#). Patients who are withdrawn from the study after the primary endpoint visit will be asked to return to the clinic for early termination assessments.

The following information will be collected:

- Concomitant medications/procedures
- AEs

The following procedures and assessments will be conducted:

- Pruritus NRS and pruritus categorical scale
- POEM
- DLQI
- EQ-5D
- Assess sick leave/missed school days
- Vital signs
- IGA
- EASI
- BSA
- Photograph AD area (select sites only)
- Weight
- Physical examination
- ECG
- Laboratory testing:
 - Hematology and chemistry

- Urinalysis
- Serum pregnancy test (WOCBP only)
[REDACTED]
[REDACTED]
- Functional dupilumab PK sample
- Anti-dupilumab antibody sample

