1.3 Modifications from the Statistical Section in the Final Protocol

Modifications from the Amended protocol 1 (final protocol)

1. concomitant medication/procedure

Any concomitant treatment is considered from the first dose of study drug in the SAP instead of the time of informed consent in the protocol.

2. Potentially clinically significant abnormality (PCSA)

PCSA is applied to clinical laboratory evaluations and vital signs in SAP, while PCSA was applied to ECG as well in the protocol.

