5.8.6 Analysis of Immunogenicity Data

5.8.6.1 Analysis of ADA Data

The incidence of ADA response variables will be summarized using descriptive statistics in the ADA population. The NAb relevant analyses will be based on all patients in the ADA population with at least one non-missing NAb result (either “NAb negative” or “NAb positive”) after first dose of the IMP.

Frequency tables of the proportion of patients developing ADA positivity in the ADA assay, Neutralizing antibody status in the NAb assay, pre-existing immunoreactivity, treatment-emergent, treatment-boosted, persistent, indeterminate and transient ADA responses and titers will be presented as absolute occurrence (n) and percent of patients (%), presented by treatment groups. Percentages are rounded to 3 significant figures; therefore, there may be slight differences between subgroups and overall percentages.

Listings of anti-dupilumab antibody status, neutralizing status, and titers per time point and treatment group will be provided.

The following summaries will be performed on the ADA population:

- Number (%) of patients ADA negative at all time points analyzed by treatment group
- ADA titers using descriptive statistics (mean, standard deviation, geometric mean, median, minimum and maximum) by treatment group
- Number (%) of patients with neutralizing antibody status (negative or positive) by treatment group
- Number (%) of patients with pre-existing ADA, treatment-emergent ADA, and treatment boosted response ADA response by treatment group
- Number (%) of patients with persistent, transient and indeterminate treatment-emergent ADA response by treatment group

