6.4 Analysis Visit Window

Data analyzed by-visit-analysis (including efficacy, laboratory data, visit sign, ECG, ADA) will be summarized by the study scheduled visits described [Appendix 10.2](#), "Schedule of Event". The analysis visit windows will be exhaustive so that all available values obtained from unscheduled visits, early termination visit (ETV) and end of treatment (EOT)/end of study (EOS) have the potential to be summarized. No analysis visit windows will be applied for the study scheduled visits.

The following analysis visit windows will be used to map the unscheduled visits, ETV and EOT/EOS visits, based on the study day:

Time window for efficacy variables

Visit No.	Visit	Targeted Study Days*	Analysis Window in Study Days		
			IGA, EASI, BSA, POEM, DLQI	EQ-5D	Sick-Leave/Missed School Days
1	Screening	<1	<1		
2	Baseline	1	1	≤1	≤1
3	Week 2	15	[2,22]		
4	Week 4	29	[23, 43]		[2, 43]
5	Week 8	57	[44, 71]	[2, 85]	[44, 71]
6	Week 12	85	[72, 99]		[72, 99]
7	Week 16 (End of Treatment)	113	[100, 127]	[86, 155]	[100, 127]
8	Week 20	141	[128, 155]		[128, 155]
9	Week 24	169	[156, 183]		[156, 183]
10	Week 28 (End of Study)	197	≥184	≥156	≥184

*Study days are calculated from 1st day of dupilumab injection (1st day of randomization if the patient is not treated)

Time window for safety variables

Visit No.	Visit	Targeted Study Days*	Analysis Window in Study Days					
			Vital Signs	Weight	ECG	Hematology and Chemistry	Urinalysis	Serum Pregnancy Test
1	Screening	<1	<1	<1	<1	<1	<1	<1
2	Baseline	1	1	1		1	1	≤1
3	Week 2	15	[2,22]					
4	Week 4	29	[23, 43]					[2, 43]
5	Week 8	57	[44, 71]			[2, 85]		[44, 71]
6	Week 12	85	[72, 99]					≥72

7	Week 16 (End of Treatment)	113	[100, 127]	[86, 155]	[86, 155]	[86, 155]	[2, 155]	[2, 155]	
8	Week 20	141	[128, 155]						
9	Week 24	169	[156, 183]						
10	Week 28 (End of Study)	197	≥ 184	≥ 156					

*Study days are calculated from 1st day of dupilumab injection (1st day of randomization if the patient is not treated)

Time window for other variables

Visit No.	Visit	Targeted Study Days*	Analysis Window in Study Days	
				PK/Drug Concentration, ADA
1	Screening	<1	<1	
2	Baseline	1	1	≤ 1
3	Week 2	15		
4	Week 4	29		
5	Week 8	57		
6	Week 12	85		[2, 99]
7	Week 16 (End of Treatment)	113	[2, 155]	[2, 155]
8	Week 20	141		
9	Week 24	169		
10	Week 28 (End of Study)	197	≥ 156	≥ 156

*Study days are calculated from 1st day of dupilumab injection (1st day of randomization if the patient is not treated)

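### On the planned visit days, a patient ADA-positive at both Week 16 and Week 28 cannot be classed as Persistent and is reported as Transient

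*SAP*

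**What the plan says.** SAP 4.5.6 divides treatment-emergent ADA responses into three classes.

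- **Persistent** requires "two or more consecutive ADA positive sampling time points separated by greater than 12-week period [greater than 85 days", with no negative or missing sample in between. Protocol 9.2.2.7 has the same rule.
- **Indeterminate** applies when the last collected sample is the only positive one.
- **Transient** is the remainder: a "treatment emergent ADA positive response that is not considered persistent or indeterminate".

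The same section states which samples are assayed: "ADA analysis will be conducted on sample collected at baseline, Week 16 (EOT), Week 28 (EOS), and ET". Protocol 10.1.2.5 also has an ADA sample drawn at Week 12, but the list in 4.5.6 omits it.

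SAP 6.4 names ADA among the by-visit data ("Data analyzed by-visit-analysis (including efficacy, laboratory data, visit sign, ECG, ADA) will be summarized by the study scheduled visits described"). Its last window table has a column headed "PK/Drug Concentration, ADA" that appears to give Week 12 a window of [2, 99].

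SAP 5.8.6.1 commits to reporting the "Number (%) of patients with persistent, transient and indeterminate treatment-emergent ADA response by treatment group".

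**The concern.** The follow-up period is 12 weeks long, and the persistence rule asks for more than 12 weeks between positives. With Week 16 and Week 28 as the only routine post-dose samples in the 4.5.6 list, the rule asks for a longer interval than the schedule provides.

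At stake is the one thing the subclassification is meant to report, which is durability. Week 28 falls 14 weeks after the last dose at Week 14. A patient already positive at Week 16 and still positive then would be tabulated with patients whose antibodies had disappeared. The SAP also does not say whether the interval is counted in nominal or actual days. If actual, two patients with the same serology could be labelled differently because one visit moved by two days.

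Evaluating immunogenicity is a stated secondary objective (Protocol 5.2, SAP 1.2.2), so a committed table on it should not carry a misleading label.

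**Working it through.** **Inputs.** Week 12 is Day 85, Week 16 is Day 113 and Week 28 is Day 197, each ±3 days (Protocol Table 1, 10.1.2.5, 10.1.2.6 and 10.1.4). The threshold and sample list are those of SAP 4.5.6. Baseline cannot supply one of the positives, because treatment-emergent requires a negative or missing baseline result.

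**The plan's own figure.** 12 × 7 = 84 days by subtraction. The bracketed 85 is reached only by counting both end days (84 + 1 = 85).

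**The routine pair.** 197 − 113 = 84 days. 84 is not greater than 85, and 84 is not greater than 84. Counted inclusively the gap is 85, which is not greater than 85. The pair fails on every count, so changing 85 to 84 alone would not help.

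**Classification on scheduled days (baseline negative or missing).**

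| Week 16 | Week 28 | As written (>85) | >84 | ≥84 |
|---|---|---|---|---|
| − | + | Indeterminate | Indeterminate | Indeterminate |
| + | − | Transient | Transient | Transient |
| + | + | Transient | Transient | Persistent |

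**Actual dates.** Each visit can fall on any of 7 days, giving 7 × 7 = 49 combinations and gaps from 194 − 116 = 78 to 200 − 110 = 90 days. The gap is 84 + k days in 7 − k combinations, for k = 0 to 6.

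- Above 85 days (k ≥ 2): 5 + 4 + 3 + 2 + 1 = 15 of 49, or 31% if all combinations are equally likely.
- At least 84 days (k ≥ 0): 7 + 6 + 15 = 28 of 49. So 21 of 49 (43%) would still fail a rule of at least 84 actual days.
- With visits peaked on the target day (assumed: 40% on the day, 20% at each of ±1, 7% at each of ±2, 3% at each of ±3, the two visits independent): P(k = 0) = 0.2516 and P(k = 1) = 0.1922. Then P(k > 0) = (1 − 0.2516)/2 = 0.3742, so the gap exceeds 85 days with probability 0.3742 − 0.1922 = 0.182. It falls short of 84 days with probability 0.374.

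**If Week 12 is analysed.** Week 12 to Week 16 is 113 − 85 = 28 days. Week 12 to Week 28 is 197 − 85 = 112 days (106 to 118 within windows).

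- Positive at Weeks 12, 16 and 28: Persistent if the span runs from first to last positive; Transient if an adjacent pair must exceed 85 days (gaps 28 and 84).
- First positive at Week 16 and still positive at Week 28: Transient on schedule under either reading.

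**Early termination samples.** Protocol 10.1.5 asks patients withdrawn before Week 16 to attend "once for early termination assessments, and again at Week 16 (primary endpoint visit"). That pair exceeds 85 days only if the ET visit is on or before Day 113 − 86 = 27, with Week 16 on target. An ET sample after Week 16 but before the Week 28 day gives a gap shorter than 84 days.

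**The case against.** The strongest reply is that the root cause is the omission of Week 12 from one sentence in SAP 4.5.6. The protocol collects that sample. The clause forbidding negative or missing samples in between also makes most sense if persistence is a first-to-last span. With Week 12 assayed, a patient positive at Weeks 12, 16 and 28 would then be Persistent. That reading of the clause is the more natural one, and it narrows the problem. It does not remove it: a patient who first becomes positive at Week 16 and stays positive is still Transient on schedule.

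Several smaller points stand in whole or in part.

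- The conflict between 4.5.6 and 6.4 is not certain. The window table is partly broken, and its Week 16 row shows [2, 155] twice. The Week 12 entry could be meant for PK only.
- SAP 6.4 already maps ET visits to windows in general. If an early ET sample shares a window with Week 16, the ET route to Persistent may not exist at all.
- A patient positive only at Week 28 is Indeterminate, so the failure to separate durable from reverted responses concerns patients already positive at Week 16.
- The planned listings by time point let a reader reconstruct each pattern.
- Both texts say the responses may be further characterized, which sounds optional. SAP 5.8.6.1, however, plans the table outright.
- The table is descriptive and no test depends on it. That limits the importance of the defect but does not make the label right.

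**Conclusion.** The concern holds. Under the sample list in SAP 4.5.6, no pattern of the two routine post-dose samples gives Persistent on the scheduled days, and patients positive at both are reported as Transient. If actual dates are used, 15 of 49 window combinations qualify: 31% with uniform visit days, 18% with the peaked distribution. Both percentages rest on assumed, independent visit timing, since the documents give none.

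The number of patients affected is unknown because the documents give no ADA incidence. The damage is limited to the persistent, transient and indeterminate breakdown. ADA positive or negative status, titer category, neutralizing status, the ADA-by-safety and ADA-by-efficacy summaries and all efficacy analyses do not use it. It should still be corrected, because the error is certain on schedule and costs little to remove.

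**What to change.** Before database lock:

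1. In SAP 4.5.6, define Persistent as treatment-emergent ADA positive at two or more consecutive analysed samples spanning at least 12 weeks by nominal visit, measured from the first to the last consecutive positive. Keep the condition on negative or missing samples in between. Week 16 plus Week 28 then qualifies whatever the drift within windows; a threshold of at least 84 actual days would not achieve this.
2. Correct or remove the 85-day figure.
3. State how an ET sample is assigned to a nominal visit for this rule.
4. Make 4.5.6 and 6.4 agree on whether the Week 12 ADA sample is analysed.
5. Add the departure from Protocol 9.2.2.7 to SAP 1.3, under "Modifications from the Amended protocol 1 (final protocol").

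The cost is wording in two SAP sections and one entry in a third. No new samples are needed, and extra assays only if the sponsor decides to analyse Week 12. If the sponsor's other dupilumab studies use the present threshold, which these documents do not show, comparisons of the persistent subclass across studies would need a footnote.

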4.6 Pharmacokinetic (PK) Variables

Pharmacokinetic variables include trough concentration (C_{trough}) over time until week 16. Samples for measurement of functional dupilumab concentration in serum will be collected before the injection of the IMP at baseline (Day 1), Week 12, Week 16 (EOT), Week 28 (EOS), ET and unscheduled visits.

A series of horizontal black bars of varying lengths, likely representing a redacted list of names or information.

5 STATISTICAL METHODS

For continuous variables, descriptive statistics will include the following: the number of patients reflected in the calculation (n), mean, median, standard deviation, minimum, and maximum.

For categorical or ordinal data, frequencies and percentages will be displayed for each category.

5.1 Demographics and Baseline Characteristics

Demographic and baseline characteristics will be summarized descriptively by treatment group based on ITT population.

5.2 Medical History and Atopic Disease Medical History

Medical history will be summarized by primary SOC and PT for each treatment group. The table will be sorted by internationally agreed order of SOC followed by PT sorted in alphabetical order based on the overall incidence across treatment groups.

Number and percentage of patients with personal history (current/past) of atopic/allergic conditions will be summarized for each treatment groups. [Appendix 10.6](#) provides a list of personal history of atopic/allergic conditions search criteria. Blinded manual adjudication will be required by the study medical monitor, before database locks.

Number and percentage of patients with family history of atopic/allergic conditions will be summarized by the categories listed on the case report form (CRF) for each treatment groups.

